Baricitinib is an oral, reversible, selective inhibitor of Janus kinase (JAK)1 and JAK2 (Fridman et al. 2010). This activity profile suggests that baricitinib may inhibit cytokines implicated in SLE, most notably type I interferon (IFN; JAK1/tyrosine kinase [TYK]2), interleukin ([IL]-6; JAK1/JAK2/TYK2), and type II IFN γ , as well as other cytokines that may have a role in SLE, including IL-23 (JAK2/TYK2), granulocyte-macrophage colony stimulating factor (JAK2/JAK2) and IL-12 (JAK2/TYK2). In a recently completed Phase 2 study (I4V-MC-JAHH [JAHH]), baricitinib demonstrated clinical efficacy in patients with SLE. Baricitinib plus standard of care was superior to placebo plus standard of care in the proportion of patients achieving remission of rash and/or arthritis as defined by the Systemic Lupus Erythematosus Disease Activity Index 2000 (SLEDAI-2K), as well as the proportion of patients achieving a Systemic Lupus Erythematosus Responder Index-4 (SRI-4) response at Week 24.

Given the efficacy of baricitinib demonstrated in clinical trials for treating autoimmune/autoinflammatory diseases involving joints, skin, and kidney (including SLE), the acceptable safety profile of baricitinib observed through the current stage of development, and a continuing unmet medical need in patients with SLE, there is a compelling rationale for the initiation of a Phase 3 program to evaluate baricitinib in the treatment of SLE.

Objective(s)/Endpoints:

Objectives	Endpoints

Primary To evaluate the long-term safety and tolerability of baricitinib in patients with SLE.
	
Safety and tolerability assessments will include:
 
 • Proportion of patients with treatment-emergent adverse events (TEAEs), adverse events of special interest (AESIs), and serious adverse events (SAEs). • Proportion of patients with temporary investigational product interruptions and permanent discontinuations.

Secondary
 
 • To evaluate the long-term effect of baricitinib 4-mg or 2-mg QD and background standard-of-care therapy on SLE disease activity. • To evaluate the long-term corticosteroid sparing effect of baricitinib 4-mg or 2-mg QD. • To evaluate the long-term effect of baricitinib 4-mg or 2-mg QD on SLE flares. • To evaluate the long-term effect of baricitinib 4-mg or 2-mg QD on mucocutaneous manifestations of SLE. 	
 • Proportion of patients achieving SRI-4 response through Week 156, defined as: 
 ○ Reduction of ≥ 4 points from baseline in SLEDAI-2K score; and ○ No new British Isles Lupus Assessment Group (BILAG) A or no more than 1 new BILAG B disease activity score; and ○ No worsening (defined as an increase of ≥ 0.3 points [10 mm] from baseline) in the Physician's Global Assessment of Disease Activity. • Proportion of patients achieving an SRI-5, -6, -7, or -8 response through Week 156. • Proportion of patients achieving an LLDAS response through Week 156. • Change from baseline in mean total SLEDAI-2K scores through Week 156. • Change from baseline in Physician's Global Disease Activity score through Week 156. • Change from baseline in prednisone dose through Week 156. • Annualized mild/moderate flare rate. • Annualized severe flare rate. • Annualized flare rate (any severity). • Proportion of patients with CLASI total activity score ≥ 10 at baseline with $\geq 50\%$ reduction in CLASI total activity score through Week 156.

Objective(s)/Endpoints:

Objectives	Endpoints

 • To evaluate the long-term effect of baricitinib 4-mg or 2-mg QD on musculoskeletal manifestations of SLE. • To evaluate the long-term effect of baricitinib 4-mg or 2-mg QD on individual organ system disease activity. • To evaluate the long-term effect of baricitinib 4-mg or 2-mg QD on damage. • To evaluate the long-term effect of baricitinib 4-mg or 2-mg QD on patient-reported outcomes (PROs). 	
 • Change from baseline in tender joint count through Week 156. • Change from baseline in swollen joint count through Week 156. • Proportion of patients with improvement in each SLEDAI-2K organ system versus baseline through Week 156. • Proportion of patients with worsening in each SLEDAI-2K organ system versus baseline through Week 156. • Change from baseline in SLICC/ACR damage index total score through Week 156. • Change from baseline in Worst Pain NRS through Week 156. • Change from baseline in Worst Joint Pain NRS through Week 156. • Change from baseline in Worst Fatigue NRS through Week 156. • Change from baseline in Patient Global Impression of Severity through Week 156. • Change from baseline in mental component score (MCS), physical component score (PCS), and domain scores in the Short-Form 36-item health survey version 2 (SF- 36v2) acute through Week 156. • Change from baseline in FACIT-F total score through Week 156. • Change from baseline in the EQ-5D-5L through Week 156. • Change from baseline in the WPAI-Lupus through Week 156.

Abbreviations: CLASI = Cutaneous Lupus Erythematosus Disease Area and Severity Index; EQ-5D-5L = 5-level EuroQol-5 Dimensions; FACIT-F = Functional Assessment of Chronic Illness Therapy-Fatigue; LLDAS = Lupus Low Disease Activity State; NRS = Numeric Rating Scale; QD = once daily; SLE = systemic lupus erythematosus; SLEDAI-2K = Systemic Lupus Erythematosus Disease Activity Index 2000; SLICC/ACR = Systemic Lupus Erythematosus International Collaborating Clinics/American College of Rheumatology; SRI-4 = Systemic Lupus Erythematosus Responder Index-4; WPAI = Work Productivity and Activity Impairment.

Summary of Study Design:

Study I4V-MC-JAIM [JAIM] is a Phase 3, multicenter, randomized, outpatient, long term extension trial to evaluate the long-term safety and efficacy of baricitinib in eligible patients with SLE who have completed the treatment period in an originating study (such as, Study I4V-MC-JAHZ [JAHZ] or Study I4V-MC-JAIA [JAIA]).

Treatment Arms and Duration:

Patients randomized to active treatment, baricitinib 4-mg daily or baricitinib 2-mg daily, during Study JAHZ or Study JAIA will continue on the same, blinded, dose of baricitinib in Study JAIM. Patients randomized to placebo during Study JAHZ or Study JAIA will be randomized 1:1 to receive baricitinib 4-mg or baricitinib 2-mg daily during Study JAIM. The treatment period will last up to 156 weeks (3 years) from enrollment into Study JAIM.

Number of Patients:

The study will enroll approximately 1100 patients.

Statistical Analysis:

Unless otherwise specified, the efficacy and health outcome analyses will be conducted on the modified intent-to-treat population, which includes patients who received at least 1 dose of investigational product in Study JAIM. Safety analyses for JAIM will be conducted on those patients who receive at least 1 dose of investigational product in JAIM who do not discontinue at the first post-baseline visit of JAIM for the reason "Lost to Follow-up".

Efficacy and health outcomes analyses will generally be summarized using descriptive statistics. The number and percentage of patients maintaining or achieving a categorical efficacy or health outcomes response will be summarized. The mean changes of the continuous measures will be summarized using mixed model repeated measures. The model will include treatment, region, visit, treatment-by-visit interaction as fixed categorical effects, and baseline value and baseline value-by-visit interaction as fixed continuous effects to estimate change from baseline across postbaseline visits. Missing data will be imputed at specified time points utilizing methodologies, including last observation carried forward and nonresponder imputation.

All safety data will be descriptively summarized by treatment group and analyzed using the safety population. Safety assessments will include adverse events, laboratory analytes, vital signs, and questionnaires to assess the existence and severity of depression. Some of the safety endpoints may be better assessed in the context of combining the safety data from the originating studies. These details will be included in the statistical analysis plan (SAP) for this study or the integrated SAP (which will detail how all Phase 2 and 3 studies will be combined).

The categorical safety measures will be summarized with percentages and incidence rates, where appropriate. The mean changes of the continuous safety measures will be summarized using descriptive statistics.

2. Schedule of Activities

Table JAIM.1. Schedule of Activities

	Baseline	Treatment Phase: Study Drug Administration											Follow-up
Visit Number	V1	V2	V3	V4	V5	V6	V7	V8	V9	V10	V11	ET ^a	V801 ^b
Study Week	W0	W4	W12	W24	W36	W48	W60	W84	W108	W132	W156	Any	W160 or last dose + 4 weeks
Study Day	1	29 ± 4	85 ± 7	169 ± 10	253 ± 10	337 ± 10	421 ± 10	589 ± 14	757 ± 14	925 ± 14	1093 ± 14	Any	Last dose + 28 ± 5 days
Procedure													
Informed consent	X												
Abbreviated patient demographics	X												
Symptom-directed physical examination	X ^c	X	X	X	X	X	X	X	X	X	X	X	X
Weight	X ^c	X	X	X	X	X	X	X	X	X	X	X	X
Waist circumference	X ^c	X	X	X	X	X	X	X	X	X	X	X	X
Vital signs (BP ^d , pulse, temperature)	X ^c	X	X	X	X	X	X	X	X	X	X	X	X
Review JAIM inclusion/exclusion criteria	X												
Adverse events	X ^e	X	X	X	X	X	X	X	X	X	X	X	X
Concomitant medications	X ^f	X	X	X	X	X	X	X	X	X	X	X	X
C-SSRS ^g & Self-Harm Supplement Form	X ^c	X	X	X	X	X	X	X	X	X	X	X	X
Self-Harm Follow-up Form ^h	X ^c	X	X	X	X	X	X	X	X	X	X	X	X
QIDS-SR16 ⁱ	X ^c	X	X	X	X	X	X	X	X	X	X	X	X
Log in IWRS	X	X	X	X	X	X	X	X	X	X	X	X	X
Randomization ^j	X												

	Baseline	Treatment Phase: Study Drug Administration											Follow-up
Visit Number	V1	V2	V3	V4	V5	V6	V7	V8	V9	V10	V11	ET ^a	V801 ^b
Study Week	W0	W4	W12	W24	W36	W48	W60	W84	W108	W132	W156	Any	W160 or last dose + 4 weeks
Study Day	1	29 ± 4	85 ± 7	169 ± 10	253 ± 10	337 ± 10	421 ± 10	589 ± 14	757 ± 14	925 ± 14	1093 ± 14	Any	Last dose + 28 ± 5 days
Investigational product dispensed	X		X	X	X	X	X	X	X	X			
Investigational product returned and compliance assessed		X ^k	X	X	X	X	X	X	X	X	X	X	
Physician-Completed Scales^l													
SLEDAI-2K	X ^c	X	X	X	X	X	X	X	X	X	X	X	X
BILAG2004	X ^c	X	X	X	X	X	X	X	X	X	X	X	X
Physician’s Global Assessment of Disease Activity	X ^c	X	X	X	X	X	X	X	X	X	X	X	X
SLEDAI Flare Index	X ^c	X	X	X	X	X	X	X	X	X	X	X	X
SLICC/ACR Damage Index	X ^c					X					X	X	
CLASI	X ^c	X	X	X	X	X					X	X	X
28-Tender and Swollen Joint Counts	X ^c	X	X	X	X	X	X	X	X	X	X	X	X
Patient-Reported Questionnaires													
Worst Pain NRS ⁱ	X	X	X	X	X	X	X	X	X	X	X	X	X
Worst Joint Pain NRS ⁱ	X	X	X	X	X	X	X	X	X	X	X	X	X
Worst Fatigue NRS ⁱ	X	X	X	X	X	X	X	X	X	X	X	X	X
Patient’s Global Impression of Severity (PGI-S) ⁱ	X	X	X	X	X	X	X	X	X	X	X	X	X
SF-36v2 ⁱ	X ^c	X	X	X	X	X	X	X	X	X	X	X	X
FACIT-Fatigue ⁱ	X ^c	X	X	X	X	X	X	X	X	X	X	X	X

	Baseline	Treatment Phase: Study Drug Administration											Follow-up
Visit Number	V1	V2	V3	V4	V5	V6	V7	V8	V9	V10	V11	ET ^a	V801 ^b
Study Week	W0	W4	W12	W24	W36	W48	W60	W84	W108	W132	W156	Any	W160 or last dose + 4 weeks
Study Day	1	29 ± 4	85 ± 7	169 ± 10	253 ± 10	337 ± 10	421 ± 10	589 ± 14	757 ± 14	925 ± 14	1093 ± 14	Any	Last dose + 28 ± 5 days
WPAI-Lupus ⁱ	X ^c	X	X	X	X	X	X	X	X	X	X	X	X
EQ-5D-5L ⁱ	X ^c	X	X	X	X	X	X	X	X	X	X	X	X
Laboratory Tests													
HBV DNA ^m	X ^c		X	X	X	X	X	X	X	X	X	X	X
Urine pregnancy test ⁿ	X ^c	X	X	X	X	X	X	X	X	X	X	X	X
Clinical chemistry ^o	X ^c	X	X	X	X	X	X	X	X	X	X	X	X
Fasting lipid panel ^p	X ^c		X	X		X			X		X		
Hematology	X ^c	X	X	X	X	X	X	X	X	X	X	X	X
Urinalysis	X ^c	X	X	X	X	X	X	X	X	X	X	X	X
Urine Creatinine and Protein, Ratio	X ^c	X	X	X	X	X	X	X	X	X	X	X	X
ANA	X ^c						X				X		
Anti-dsDNA	X ^c	X	X	X	X	X	X	X	X	X	X	X	X
Autoantibodies (anti-Smith, anti-RNP, anti-SSA/Ro, anti-SSB/La)	X ^c					X					X		
Anti-cardiolipin antibodies IgG, IgA, IgM)	X ^c					X					X	X	X
Anti-beta2 glycoprotein-I (IgG, IgM)	X ^c					X					X	X	X
Lupus anticoagulant (dRVVT)	X ^c					X					X	X	X

	Baseline	Treatment Phase: Study Drug Administration											Follow-up
Visit Number	V1	V2	V3	V4	V5	V6	V7	V8	V9	V10	V11	ET ^a	V801 ^b
Study Week	W0	W4	W12	W24	W36	W48	W60	W84	W108	W132	W156	Any	W160 or last dose + 4 weeks
Study Day	1	29 ± 4	85 ± 7	169 ± 10	253 ± 10	337 ± 10	421 ± 10	589 ± 14	757 ± 14	925 ± 14	1093 ± 14	Any	Last dose + 28 ± 5 days
Complement (C3 and C4)	X ^c	X	X	X	X	X	X	X	X	X	X	X	X
Immunoglobulins (IgG, IgA, IgM)	X ^c					X					X	X	X
Exploratory storage samples (serum and plasma)	X ^c					X					X		
Exploratory storage samples (urine)	X ^c					X					X		

Abbreviations: ANA = antinuclear antibody; BILAG = British Isles Lupus Assessment Group; BP = blood pressure; CLASI = Cutaneous Lupus Erythematosus Disease Area and Severity Index; C-SSRS = Columbia-Suicide Severity Rating Scale; dRVVT = Dilute Russell's Viper Venom Time; dsDNA = double-stranded deoxyribonucleic acid; EQ-5D-5L = 5-level EuroQol-5 Dimensions; ET = early termination; FACIT = Functional Assessment of Chronic Illness Therapy; HBcAb = hepatitis B core antibody; HBsAb = hepatitis B surface antibody; HBV DNA = hepatitis B virus deoxyribonucleic acid; Ig = immunoglobulin; IWRS = interactive web-response system; NRS = numerical rating scale; PGI-S = Patient's Global Impression of Severity; RNP = ribonucleoprotein; QIDS-SR16 = 16-Item Quick Inventory of Depressive Symptomatology-Self Report; SF-36v2 = Short-Form 36-item Health Survey version 2; SLE = systemic lupus erythematosus; SLEDAI-2K = Systemic Lupus Erythematosus Disease Activity Index 2000; SLICC/ACR = Systemic Lupus Erythematosus International Collaborating Clinics/American College of Rheumatology; SSA/Ro = Sjögren's-Syndrome-related antigen A; SSB/La = Sjögren syndrome type B antigen/Lupus La protein; V = visit; W = week; WPAI = Work Productivity and Activity Impairment.

- ^a Patients who discontinue from investigational product (IP) early should complete the ET visit and proceed to post-treatment follow-up.
- ^b All patients should return for Visit 801, a post-treatment follow-up visit, 28±5 days after the last dose of IP. Patients who discontinue IP but remain in the study for at least 28±5 days without IP, can combine their Visit 11/ET with their Visit 801 (post-treatment follow-up visit).
- ^c Visit 1 of Study JAIM should occur on the same day as the final visit of the originating study. Assessments/procedures required for both Visit 1 of Study JAIM and the final visit of the origination study should only be performed once.
- ^d At each time point, 3 replicate readings should be made at approximately 30- to 60-second intervals. Blood pressure is recorded as the average of these 3 readings. A single pulse measurement should be made simultaneously with at least 1 of the readings at each time point (Section 9.4.1. for details on vital signs).
- ^e Adverse events that are ongoing at the completion of the originating trial should be reported as pre-existing conditions at Visit 1 for Study JAIM.
- ^f Concomitant medications ongoing at the completion of the originating trial should be reported as concomitant medications at Visit 1 for Study JAIM.
- ^g Suicidal ideation and behavior subscales excerpt; adapted for the assessment of 11 preferred ideation and behavior categories. C-SSRS and Self-Harm Supplemental Form should be completed after collection of unsolicited adverse events.
- ^h The Self-Harm Follow-up Form is only required if triggered by the Self-Harm Supplement Form.
- ⁱ Patient-reported questionnaires will be administered via an on-site electronic clinical outcome assessment (eCOA) device and should be administered prior to any clinical assessments.
- ^j At Visit 1, patients randomized to active treatment during the originating study will be assigned to the same, blinded dose of baricitinib in Study JAIM. Patients randomized to placebo during the originating study will be randomized 1:1 to blinded baricitinib 2-mg or baricitinib 4-mg. Dose adjustment for patients newly randomized to baricitinib, if necessary, will be based on the last available estimated glomerular filtration rate (eGFR) from the originating study.
- ^k New bottles of study drug tablets will NOT be dispensed at Week 4 (Visit 2) unless the patient requires additional tablets for the next visit window. Patients will continue to take tablets from the bottles dispensed at Week 0 (Visit 1). Compliance will be checked, and the bottles with remaining tablets will be returned to the patient for dosing the following visit window. If new bottles are required, the patient will not have their previous bottles returned.
- ^l SLE assessments must be completed by a physician and will be documented on an eCOA (electronic clinical outcome assessment) device.
- ^m Patients who were enrolled in the originating study with positive HBcAb and negative HBV DNA, regardless of HBsAb status or level, must undergo HBV DNA testing per the schedule of events (see Section 9.4.6 for details of HBV DNA monitoring).

- ⁿ For all women of childbearing potential, urine pregnancy tests (local laboratory) will be performed at all study visits. If required per local regulations and/or institutional guidelines, pregnancy testing can occur more frequently during the study treatment period. Unscheduled urine pregnancy tests may also be performed if a regular monthly menstruation is absent in a woman of childbearing potential.
- ^o Clinical chemistry will include the following value calculated from serum creatinine: eGFR (calculated using the Modification of Diet in Renal Disease [MDRD] isotope dilution mass spectrometry traceable method).
- ^p Patients should not eat or drink anything, except water, for 12 hours prior to sample collection. If a patient attends these visits in a nonfasting state, the sample should still be collected. This will not be considered a protocol violation.

3. Introduction

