Follow-Up Period: Patients who complete the treatment period, as well as those who discontinue JAIM study treatment early, will have a post-treatment follow-up visit (Visit 801) approximately 4 weeks after the last dose of investigational product.

Abbreviations: QD = once daily; V visit

- a. Visit 1 of Study JAIM should be completed on the same calendar day as the Week-52 visit of the originating study.
- b. The follow-up visit should occur 4 weeks (± 5 days) after the last dose of study drug.

Figure JAIM.1. Illustration of study design for Clinical Protocol I4V-MC-JAIM.

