**Table JAIM.6.5. Definition of Postbaseline Period**

Analysis Population	Treatment Groups (Short Label)	Postbaseline Time Period
Safety Population	See Table JAIM.6.1	
For all analyses except the “by-visit” continuous analysis: From immediately after first dose of baricitinib in Study JAIM and ending at the earliest of
 
 
• 30 days after last dose date of study drug
 
• the study disposition date, or
 
• the cut-off date if subject is on treatment.
 
 
For the “by-visit” continuous analyses: Includes planned/scheduled measurements after first dose of baricitinib up to last visit, excluding the follow up visit.

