**Table JAIM.6.6. Summary Tables Related to Adverse Events**

Analysis
Listing of adverse events leading to permanent discontinuation of study drug and discontinuation from the study
Listing of deaths
Listing of SAEs
Listing of Opportunistic Infections
Overview of AEs
Overview of Infections
The number and percentage of patients with TEAE using MedDRA Preferred Term nested within SOC
The number and percentage of patients who permanently discontinued from study drug due to an adverse event (including adverse events that led to death) using MedDRA Preferred Term nested within SOC
The number and percentage of patients reporting SAEs using MedDRA Preferred Term nested within SOC
The number and percentage of patients with at least one temporary interruption of study drug.

Abbreviations: AE = adverse event; PT = Preferred Term; SAE = serious adverse event; SOC = System Organ Class; TEAE = treatment-emergent adverse event.

A treatment-emergent AE (TEAE) is defined as an event that first occurred or worsened in severity after the first dose of study treatment in Study JAIM and on or prior to the last visit date during the analysis period. The analysis period is defined as the treatment period plus up to 30 days off-drug follow-up time.

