### **6.14.3. Clinical Laboratory Evaluation**

For the categorical analysis, the analysis period is defined as the treatment period plus up to 30 days off-drug follow-up time. The analysis period for the continuous by-visit analyses (eg, change from baseline by visit) is defined as the treatment period excluding off-drug follow-up time. Refer to the iSAP for more details. The following analyses are planned:

- clinical laboratory evaluation in terms of box plots and treatment-emergent summaries.

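### The follow-up visit may fall up to Day 33 after the last dose but the SAP's safety period stops at Day 30, so laboratory and vital-sign results from a compliant late visit miss the JAIM-alone treatment-emergent summaries

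*Protocol*

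**What the plan says.** **Protocol.** The timing of Visit 801 is given three times, consistently. The header of Table JAIM.1 (Section 2) has "Last dose + 28 ± 5 days". Footnote b of that table has "All patients should return for Visit 801, a post-treatment follow-up visit, 28±5 days after the last dose of IP". The note to Figure JAIM.1 (Section 5.1) has "The follow-up visit should occur 4 weeks (± 5 days) after the last dose of study drug". Table JAIM.1 schedules adverse events, vital signs, chemistry, hematology and urinalysis at this visit. Footnote b also lets patients who stay in the study off drug for at least that interval combine Visit 11 or the early termination visit with Visit 801.

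**SAP.** Section 6.14 refers to Table JAIM.6.5 for the safety postbaseline period. For all analyses except the by-visit continuous ones, the period ends at the earliest of three dates: "30 days after last dose date of study drug", the study disposition date, or the data cut-off if the patient is still on treatment. Section 6.14.3 (laboratory) repeats the limit: "For the categorical analysis, the analysis period is defined as the treatment period plus up to 30 days off-drug follow-up time". Section 6.14.4 (vital signs) says the same. The by-visit continuous analyses leave Visit 801 out on any day: "Includes planned/scheduled measurements after first dose of baricitinib up to last visit, excluding the follow up visit".

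Under Table JAIM.6.6, Section 6.14.1 sets two conditions for a treatment-emergent adverse event (TEAE). It is "defined as an event that first occurred or worsened in severity after the first dose of study treatment in Study JAIM", and its onset or worsening must also be "on or prior to the last visit date during the analysis period". The analysis period there is again treatment plus up to 30 days.

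**The concern.** The collection window and the analysis window do not match. Two patients can both attend Visit 801 within protocol, one on Day 30 and one on Day 31, and have the same new laboratory abnormality. The first enters the treatment-emergent summary and the second does not. Only the appointment date separates them. The omission works in one direction, because it can lower the count of treatment-emergent findings but never raise it.

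Visit 801 is the only visit of the Follow-Up Period, and long-term safety is the study's primary objective. The JAIM-alone laboratory and vital-sign summaries should not lose scheduled data for a reason unrelated to the patient's condition.

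**Working it through.** **1. The visit window.** 4 weeks × 7 = 28 days. 28 − 5 = 23 and 28 + 5 = 33. The three protocol statements agree on Days 23 to 33 after the last dose, which is 33 − 23 + 1 = 11 whole days.

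**2. Against the SAP limit.** Days 31, 32 and 33 lie beyond last dose + 30. That is 3 of 11 permitted days, or 27.3%.

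**3. Does another rule bring such a visit back in?** SAP 6.3 defines safety postbaseline measurements, outside the by-visit analyses, without an upper limit. But 6.14 names Table JAIM.6.5 as the definition of the period, and 6.14.3 and 6.14.4 each state 30 days. The specific rules govern. If a programmer followed 6.3 instead, the SAP would contradict itself and would still need correcting.

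**4. What a compliant visit on Day 32 loses.**

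| Data from the visit | Treatment under the SAP |
|---|---|
| Laboratory and vital signs, categorical summaries | Left out; the same results on Day 30 would be included |
| Laboratory and vital signs, by-visit continuous analyses | Left out on any day, so nothing further is lost |
| Adverse event with onset up to Day 30, reported at this visit | Counted under Table JAIM.6.5, which goes by onset |
| Adverse event with onset or worsening on Days 31 to 33 | Not counted under Table JAIM.6.5 |

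**5. The end rule in 6.14.1.** Read literally, a Day 32 visit is not a visit during the analysis period, so the last visit within it is an earlier one. For a completer that is typically Visit 11, nominally Day 1093, where Table JAIM.3 has dosing through Day 1092: one day off drug. Onsets after that day would then drop out, including those up to Day 30 that Table JAIM.6.5 counts. The two rules give different answers for the same event.

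**6. Share of compliant visits affected.** The documents give no distribution of visit dates, so this rests on assumption. Take visit days as normal around Day 28 with standard deviation s, rounded to whole days and restricted to Days 23 to 33. With F the cumulative distribution, share = [F(33.5) − F(30.5)] / [F(33.5) − F(22.5)].

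| Assumed s (days) | Numerator | Denominator | Share beyond Day 30 | Per 1100 visits |
|---|---|---|---|---|
| 1.5 | 0.0477 | 0.9998 | 4.8% | 52 |
| 2.5 | 0.1448 | 0.9722 | 14.9% | 164 |
| 3.5 | 0.1795 | 0.8839 | 20.3% | 223 |
| Uniform over the window | 3 | 11 | 27.3% | 300 |

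The last column uses the planned enrolment of about 1100 and supposes that every patient attends in window, so it is an upper illustration. It counts visits, not events.

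**7. After the change.** With a limit of 33 days, 0 of the 11 permitted days fall outside.

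**The case against.** How long after stopping drug a finding still counts as treatment-emergent is a convention. Thirty days contains the Day 28 target, and the added days are those least attributable to drug. The JAIM-alone safety tables are descriptive, with no between-arm test, and nothing suggests that visit timing differs by arm. A patient already abnormal on treatment is already counted; only a first abnormality appearing at a Day 31 to 33 visit changes a table. All of this stands, and it keeps the point small. It does not explain why two compliant visits should be treated differently.

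Four stronger readings are tempting, and the documents do not support them:

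- **All the visit's adverse event data are lost.** Under Table JAIM.6.5 the date of onset or worsening decides, not the visit at which the event is reported. Only the wording of 6.14.1 opens a wider loss.
- **The data vanish from all safety reporting.** They are still collected. The SAP states no 30-day limit specific to the listings of serious adverse events and deaths, and the registry summary in SAP 6.19 counts serious events whether or not they are treatment-emergent.
- **Exclusion from the by-visit continuous analyses adds to the loss.** It is a deliberate on-treatment choice that applies to Visit 801 on any day.
- **The primary safety analysis is biased.** Protocol 10.3.4 and SAP 6.14 place it in the integrated safety analysis plan, which is not available here, so its window cannot be checked.

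**Conclusion.** The mismatch is certain: Day 33 against Day 30, with no SAP rule to close the gap. Its demonstrated effect is limited to the JAIM-alone categorical laboratory and vital-sign summaries and to adverse events starting or worsening on Days 31 to 33. The separate end rule in 6.14.1 conflicts with Table JAIM.6.5 and leaves open a larger loss of off-drug adverse events if programmed literally.

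About 5% to 20% of compliant visits would be affected if they centre on Day 28 with the assumed spread, and 27% if spread evenly over the window. How many findings this removes cannot be derived from the documents; it is probably few. This is a minor point, worth correcting because the correction is simple and exact.

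**What to change.** In the SAP:

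1. In Table JAIM.6.5 and Sections 6.14.1, 6.14.3 and 6.14.4, set the off-drug limit to 33 days, the upper end of the Visit 801 window.
2. In 6.14.1, end the TEAE period where the Table JAIM.6.5 period ends, rather than at the last visit within it.
3. State how a combined Visit 11 or early termination visit and Visit 801 held after Day 33 is handled. Footnote b gives it no upper day, so the 33-day limit alone does not cover it.

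The cost is SAP wording and one date constant. The downside is up to 3 more off-drug days per patient, and the integrated safety analysis plan should use the same limit so that the two sets of tables agree. No visit, procedure or treatment rule changes.
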